Radiologic integration of the HPTC scaffold was evaluated using a predefined MRI Integration Score (MIS), a composite semi-quantitative scoring system developed to assess biological scaffold performance. MRI examinations were performed immediately postoperatively and at 4 and 8 weeks using standardized T1-weighted, T2-weighted, and dynamic contrast-enhanced sequences.

The MIS evaluated four domains: scaffold–host tissue integration, neovascularization based on enhancement patterns, scaffold resorption and volume replacement, and tissue quality within the scaffold region. Each domain was scored from 0 to 3, yielding a total score ranging from 0 to 12, with higher scores indicating superior integration and regenerative remodeling.

Cosmetic Outcome: BREAST-Q

Cosmetic outcomes were assessed using the BREAST-Q questionnaire [14], a validated patient-reported outcome measure specific to breast surgery. The “Satisfaction with Breasts” domain was prespecified as the primary cosmetic endpoint. Questionnaires were administered preoperatively and at 4 and 8 weeks postoperatively. Raw scores were converted to standardized scores ranging from 0 to 100 according to BREAST-Q scoring manuals, with higher scores indicating greater satisfaction [14].

Improvement over baseline and attainment of an absolute score ≥ 70 at final follow-up were considered clinically meaningful cosmetic outcomes.

Safety and Complications

Safety assessment included prospective recording of all adverse events and postoperative complications, including seroma, surgical site infection, hematoma, wound dehiscence, scaffold migration or exposure, and delays in adjuvant oncologic therapy. Device-related serious adverse events were specifically monitored. All events were managed according to institutional protocols and documented throughout the follow-up period.

Data Collection and Follow-up

Baseline demographic data, tumor characteristics, operative details, and immediate postoperative imaging were recorded at enrollment. Follow-up assessments were conducted at 2, 4, and 8 weeks postoperatively, during which volumetric measurements, MRI evaluation, BREAST-Q questionnaires [14], and complication surveillance were completed. Data were recorded in standardized case record forms at both centers to ensure uniformity.

Statistical Analysis Plan

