Statistical analysis was performed using IBM SPSS Statistics (version 28.0). Continuous variables were summarized as mean \pm standard deviation, while categorical variables were expressed as frequencies and percentages. Longitudinal changes in breast volume retention, MRI Integration Score, and BREAST-Q scores were analyzed using repeated-measures analysis of variance. One-sample t-tests were used to compare observed volume retention against predefined clinical benchmarks. Correlations between objective volumetric outcomes and patient-reported satisfaction were assessed using Pearson correlation coefficients. A two-sided p value of less than 0.05 was considered statistically significant.

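### BREAST-Q improvement is the stated cosmetic outcome, but no preoperative-to-week-8 contrast or confidence interval is prespecified; the ANOVA time-effect p-value does not test it

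*Combined protocol and SAP*

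**What the plan says.** In the section Cosmetic Outcome: BREAST-Q, the Satisfaction with Breasts "domain was prespecified as the primary cosmetic endpoint". The schedule there has three time points: "Questionnaires were administered preoperatively and at 4 and 8 weeks postoperatively". The outcome is then defined: "Improvement over baseline and attainment of an absolute score ≥ 70 at final follow-up were considered clinically meaningful cosmetic outcomes".

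The Statistical Analysis Plan is one paragraph. For BREAST-Q change it says: "Longitudinal changes in breast volume retention, MRI Integration Score, and BREAST-Q scores were analyzed using repeated-measures analysis of variance". Two other inferential methods appear, and neither fills the gap. One is confined to volume: "One-sample t-tests were used to compare observed volume retention against predefined clinical benchmarks". The other measures association, not change: "Correlations between objective volumetric outcomes and patient-reported satisfaction were assessed using Pearson correlation coefficients". Means with SDs, and frequencies with percentages, are planned as descriptive summaries.

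**The concern.** Improvement over the preoperative score at the end of follow-up is a directional question about two time points: week 8 minus preoperative. A repeated-measures ANOVA with no named contrast yields an overall test of whether any of the visit means differ, in any direction. A temporary fall at week 4 followed by full recovery satisfies that test as well as a real gain does. Such a dip is plausible, because week 4 comes soon after cancer surgery and adjuvant treatment may have begun.

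The named primary cosmetic endpoint could therefore be reported as showing a significant change over time, next to a week-8 mean slightly above the preoperative one, when the true net change is zero. The trial also says that it aims to estimate effect sizes for later definitive trials. An F statistic gives no effect size for BREAST-Q improvement. Visit-wise SDs do not give the uncertainty of a paired change either, since that depends on the between-visit correlation.

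**Working it through.** The documents give no power, precision or SD for BREAST-Q, so there is no stated figure to reproduce. The 10% SD in Sample Size Determination belongs to volume retention.

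**Inputs from the documents.** n = 40 (Sample Size Determination), all taken as complete; visits preoperative, week 4 and week 8 (BREAST-Q section); two-sided 0.05 (Statistical Analysis Plan).

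**Assumptions.** SD 15 to 20. Either a common between-visit correlation of 0.3 to 0.7, or an unequal pattern with 0.4 between preoperative and each later visit and 0.8 between weeks 4 and 8. The mean profiles are illustrative.

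**Step 1: what each test asks.** The F test's null hypothesis is that all three visit means are equal. The stated outcome concerns only the week-8 mean minus the preoperative mean.

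**Step 2: how often F is significant with no net change.** With a common correlation ρ, F has 2 and 2 × 39 = 78 degrees of freedom and noncentrality λ = n Σ(mean at visit − overall mean)² / [SD² (1 − ρ)].

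- 60-50-60: overall mean 56.67, sum of squares 3.33² + 6.67² + 3.33² = 66.7, times 40 = 2,667.
- 60-54-60: overall mean 58, sum of squares 4 + 16 + 4 = 24, times 40 = 960.

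| SD, ρ | SD²(1 − ρ) | λ, 60-50-60 | F significant | λ, 60-54-60 | F significant |
|---|---|---|---|---|---|
| 20, 0.3 | 280 | 9.5 | about 78% | 3.4 | about 34% |
| 15, 0.7 | 67.5 | 39.5 | about 100% | 14.2 | about 92% |

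Simulation agrees, and the unequal pattern falls inside these ranges.

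**Step 3: a fairer count.** The planned means show direction, so the misleading result is a significant F together with a week-8 mean above the preoperative mean. When the two true means are equal and the correlations are common, the observed difference is equally likely to fall either way. The rates therefore halve: 78/2 = 39% to 100/2 = 50%, and 34/2 = 17% to 92/2 = 46%. Simulation gives about 38-51% for 60-50-60 and 17-46% for 60-54-60.

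**Step 4: the direct contrast.** A paired t statistic on week 8 minus preoperative (39 degrees of freedom), two-sided at 0.05, shows a significant gain in 5%/2 = 2.5% of trials when the net change is zero. The depth of the dip, the SD and the correlation do not alter this.

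**Step 5: precision of the direct contrast.** The SD of the change is SD × √[2(1 − ρ)]. At SD 18 and ρ = 0.5 this is 18, and the 95% half-width is about 2.02 × 18/√40 = 5.8 points. Over preoperative-to-week-8 correlations of 0.4 to 0.7 it runs from about 6.3 down to 4.4 points.

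**The case against.** The strongest reply is that repeated-measures ANOVA is not a wrong method. It admits contrasts: with three visits scored equally, its linear component is exactly week 8 minus preoperative. The plan never says that only the overall test will be used; that is inferred from its silence. This stands, and it makes the defect an unspecified contrast. It does not remove the defect, because pairwise comparisons chosen after the data are seen leave both the comparison and any multiplicity adjustment open.

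A reader might infer that the plan would let a net fall in satisfaction pass as a benefit. The documents do not support that. The planned means show direction: with true means of 60-52-55, a significant F with the week-8 mean above preoperative occurs in only about 0.2-2% of trials. A two-sided week-8 contrast would itself be significant on that fall in 26-76%.

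A reader might also infer that the ANOVA wastes power. That cuts both ways. For a steady gain of 60-64-68 at SD 18, the contrast has 71-94% power against 64-90% for F. For a gain that comes wholly after week 4, F has the advantage.

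The outcome sentence can be read as describing individual patients, summarised by percentages, and it is unclear whether the final-follow-up timing governs improvement as well as the score of 70. Both ambiguities are real. If the timing is open, the need for a stated contrast is greater. Similarly, Data Collection and Follow-up can be read as adding a week-2 questionnaire ("Follow-up assessments were conducted at 2, 4, and 8 weeks postoperatively, during which volumetric measurements, MRI evaluation, BREAST-Q questionnaires"); a fourth visit would make the overall test less specific still.

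Finally, this is a feasibility and early efficacy trial, BREAST-Q is outside the primary composite, and no success decision hangs on its p-value. That limits the weight of the point.

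**Conclusion.** The point holds as a gap in specification. The named primary cosmetic endpoint has no prespecified estimate, interval or test of change from preoperative to week 8, and the time-effect p-value does not supply one.

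Under a dip with full recovery, a significant F with an apparently higher week-8 mean arises in about 17-51% of trials across the two profiles, against about 2.5% for a significant gain on the direct contrast. These rates rest on assumed SDs, correlations and dip depths and on complete data. The non-directional nature of the overall F test rests on none of them.

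It would go too far to say that the ANOVA cannot accompany evidence of improvement, that it would disguise a decline, or that it is the less powerful choice in general. The point does not touch the primary composite endpoint. It should be corrected because the remedy is nearly free.

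**What to change.** Keep BREAST-Q in the ANOVA sentence of the Statistical Analysis Plan as a supportive description of the time course, and add:

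> The main BREAST-Q analysis is the mean change in Satisfaction with Breasts from preoperative to week 8 with a two-sided 95% CI (paired comparison, or the same contrast from the repeated-measures model). Improvement is claimed only if the lower limit is above 0.

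The cost is two sentences and no new data. The downside is somewhat less power than the F test if the whole gain occurs after week 4. For an 8-point gain at SD 18, the contrast has about 78% against 81% at correlation 0.5, and 71% against 86% under the unequal pattern (0.4/0.4/0.8).

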The trial was conducted in accordance with the principles of the Declaration of Helsinki and Good Clinical Practice guidelines. Approval was obtained from the Institutional Ethics Committees of both participating centers prior to patient enrollment. Written informed consent was obtained from all participants. The methodological framework, outcome hierarchy, and statistical rigor were modeled on previously published multicenter HPTC trials to ensure internal validity and reproducibility.

Patient Selection and Eligibility Criteria

Women aged 18 to 70 years undergoing BCS for stage 0–II breast carcinoma or high-risk premalignant breast lesions were screened for eligibility. Patients were required to have a unifocal lesion suitable for wide local excision with an anticipated postoperative breast volume deficit of at least 20%, as estimated intraoperatively by the operating surgeon. Adequate skin envelope viability and the ability to undergo serial MRI examinations were mandatory.

Exclusion criteria included multicentric disease requiring mastectomy, prior radiotherapy to the ipsilateral breast, active local or systemic infection, known hypersensitivity to collagen-based products, autoimmune or connective tissue disorders, uncontrolled systemic illness, pregnancy or lactation, and inability to comply with postoperative follow-up or patient-reported outcome assessments.

Sample Size Determination

This study was designed as a prospective feasibility and early efficacy trial. Sample size was determined based on precision estimation for the primary composite endpoint rather than traditional hypothesis testing. Assuming a true success rate of 75% (based on oncoplastic literature), a sample of 40 patients provides an expected 95% confidence interval width of approximately 25%, which was deemed acceptable for preliminary efficacy assessment and effect size estimation to inform future definitive trials. The sample size also ensures adequate power (>80%) to detect a clinically meaningful difference of 15% in volume retention compared to the benchmark of 75%, assuming a standard deviation of 10% and $\alpha = 0.05$.

Surgical Technique and Intervention

All patients underwent standard oncologic breast-conserving surgery performed by experienced breast or plastic surgeons at the respective centers. Following tumor excision with confirmed hemostasis and margin adequacy, the excision cavity was carefully assessed for volume deficit and three-dimensional geometry.

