A high purity Type I collagen scaffold was trimmed intraoperatively to conform precisely to the dimensions of the surgical cavity and implanted without tension. The scaffold was positioned in direct contact with surrounding viable breast tissue to facilitate cellular infiltration and neovascularization. No additional fixation beyond absorbable sutures was routinely required. Layered parenchymal and skin closure was performed using standard techniques. The use of surgical drains was left to the discretion of the operating surgeon based on oncologic considerations rather than scaffold placement.

Postoperative management, including antibiotics, wound care, chemotherapy, and radiotherapy, followed institutional breast cancer treatment protocols.

Outcome Measures

Primary Outcome: Breast Volume Restoration Success

The primary efficacy endpoint was breast volume restoration success at two months postoperatively, defined as a composite outcome incorporating both objective volumetric preservation and patient-perceived cosmetic satisfaction. Success required achievement of at least 80% objective breast volume retention relative to the immediate postoperative baseline, together with a patient satisfaction score of ≥ 7 on a 10-point Likert scale. This composite

endpoint was selected to ensure that structural volume preservation translated into clinically meaningful cosmetic benefit and patient acceptance.

Objective Breast Volume Retention

Objective breast volume retention was assessed using a dual-modality approach comprising three-dimensional surface photogrammetry and magnetic resonance imaging (MRI) volumetry. Baseline measurements were obtained within 48 hours postoperatively and repeated at 2, 4, and 8 weeks. Breast volumes were calculated for the operated breast and normalized against the immediate postoperative volume to derive percentage volume retention. MRI volumetry served as the reference standard, while 3D surface imaging provided adjunctive validation and assessment of symmetry.

Volume retention was expressed as a continuous variable and analyzed longitudinally to assess temporal stability and controlled scaffold resorption.

MRI Integration Score (MIS)

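### The only planned analysis linking retained volume to satisfaction is an unadjusted correlation: it leaves out the preoperative BREAST-Q score and is open to confounding by deficit size

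*Combined protocol and SAP*

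**What the plan says.** The Statistical Analysis Plan gives the link between volume and satisfaction one sentence: "Correlations between objective volumetric outcomes and patient-reported satisfaction were assessed using Pearson correlation coefficients". It names no covariate, visit or satisfaction instrument, and does not say whether scores are absolute or changes from baseline. The same section sets the general threshold: "A two-sided p value of less than 0.05 was considered statistically significant".

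Four other places bear on it:

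- Objective Breast Volume Retention: the operated breast's volume is divided by its own immediate postoperative volume, that is, with the scaffold already in place. Some scaffold resorption is expected.
- Patient Selection and Eligibility Criteria: entry requires an "anticipated postoperative breast volume deficit of at least 20%, as estimated intraoperatively by the operating surgeon". This is a floor without a ceiling, and deficit size enters no analysis.
- Cosmetic Outcome: BREAST-Q: "Questionnaires were administered preoperatively and at 4 and 8 weeks postoperatively". Improvement over baseline is a stated outcome, and the Statistical Analysis Plan analyses BREAST-Q over time by repeated-measures ANOVA.
- Primary Outcome: the composite pairs retention with a separate 10-point satisfaction score, for which no preoperative value is described. It was chosen to "ensure that structural volume preservation translated into clinically meaningful cosmetic benefit and patient acceptance".

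**The concern.** The composite counts women who meet both criteria. It cannot show whether one criterion is related to the other, so the correlation is the only stated evidence on that relation. Two weaknesses follow from leaving it unadjusted.

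First, deficit size may act on both variables. A scaffold filling a larger cavity is a larger share of the breast, so the same proportional resorption takes more off whole-breast retention. The Introduction itself says that tissue loss can compromise cosmetic outcome. A positive coefficient could then arise with no effect of retention, and a rank correlation would have the same fault.

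Second, women differ in satisfaction before surgery. If that carries over to week 8, it is noise that the plan could remove with a score it already collects.

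At stake is how a significant coefficient is read, and how well a real association is estimated, in a trial meant to inform later ones.

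**Working it through.** **1. The plan's own figures.** The sample size section says that "a sample of 40 patients provides an expected 95% confidence interval width of approximately 25"%, at 75% success. The Wald width is 2 × 1.96 × √(0.75 × 0.25/40) = 26.8%, and the expected width is 25.6% (Wilson) or 26.4% (Wald), so the figure is reproduced. The section also claims "adequate power (>80%) to detect a clinically meaningful difference of 15% in volume retention compared to the benchmark of 75"%. With SD 10% that power is above 99.9%, so the claim holds. Neither figure concerns the correlation, for which none is given. By Fisher's z with 40 women (SE = 1/√37 = 0.164), significance needs |r| of about 0.31 and 80% power needs r of about 0.43. With 36 or 32 evaluable women the latter becomes 0.45 or 0.48.

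**2. Retention and deficit.** Let d be the scaffold's share of the filled breast and f the share of scaffold volume lost by week 8, with no other volume change (a simplification). Retention = 100(1 − d·f). At f = 0.5:

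- d = 0.20 gives 90%
- d = 0.40 gives 80%
- d = 0.50 gives 75%

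**3. False positives when retention has no effect.** If deficit correlates −a with retention and −b with satisfaction, the expected raw correlation is a·b.

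Assumed, not in the documents: d uniform on 0.20–0.40 or 0.20–0.50; f with mean 0.5 and SD 0.15–0.25, independent of d; measurement SD 3–4 points; b = 0.3–0.5. Then Var(R) = 100²[E(d²)E(f²) − (E(d)E(f))²] + error², and a = 0.5 × SD(d)/SD(R), in percentage points.

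- Weak case (d to 0.40, SD of f 0.25, error 4, b = 0.3): SD(d) = 5.77, SD(R) = 9.1, a = 0.32, r = 0.095.
- Strong case (d to 0.50, SD of f 0.15, error 3, b = 0.5): SD(d) = 8.66, SD(R) = 7.55, a = 0.57, r = 0.287.

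The chance of p < 0.05 is Φ(atanh(r)√37 − 1.96) + Φ(−atanh(r)√37 − 1.96), which is 9% and 43%. Simulating 3,000 trials per scenario gives about 9% to 45%. Adjusting for the preoperative score and a surgeon's estimate with 5-point error brings this to about 5–10% in most scenarios and 14% in the worst. With the true deficit it is about 5%. Where retention SD is near the plan's 10%, the raw rate is 13–27% and the adjusted rate 5–8%.

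**4. Precision from the preoperative score.** Assume a standardised retention effect of 0.35, no deficit effect, and a preoperative score independent of retention and correlated ρ with the outcome. The partial correlation is 0.35/√(1 − ρ²), with √36 in place of √37.

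| ρ | partial r | power by Fisher's z | power by simulation |
|---|---|---|---|
| raw, no covariate | 0.350 | 60% | about 61–62% |
| 0.5 | 0.404 | 73% | about 74% |
| 0.3 | 0.367 | 64% | about 65% |
| 0 | 0.350 | 59% | about 1 point below raw |

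**5. Cost of adding deficit.** A surgeon's estimate with 5-point error correlates with retention at a′ = a × SD(d)/√(SD(d)² + 25), in size 0.24 (weak case) and 0.50 (strong case). If neither covariate relates to satisfaction, the partial r is 0.35√(1 − a′²)/√(0.35²(1 − a′²) + 1 − 0.35²) = 0.341 and 0.309. With √35, power is 56% and 47% against 60% raw, a loss of about 4 to 13 points.

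**6. Baseline adjustment and bias.** Adjusting for the preoperative score alone turns a·b into a·b/√(1 − ρ²). At ρ = 0.5 the weak and strong cases become 0.110 and 0.331, and false positives 10% and 54% against 9% and 43% raw. It removes noise and leaves the bias in place.

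**The case against.** The strongest reply is that this is a supporting analysis in a feasibility trial. The plan says only that correlations were assessed. No causal claim, hypothesis or power statement rests on them, and the sentence about volume translating into benefit justifies the composite, not the correlation. All of that stands, and it limits the point to a secondary analysis.

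A reader might infer that the correlation is confounded. The documents do not show that. They give no spread of deficits, no scaffold loss and no deficit-satisfaction association, and the retention formula is a simplification. The top of the 9–45% range needs deficits up to 50% and a deficit-satisfaction correlation of −0.5. If mean retention is about 90% with SD 8–9, raw false positives are 7–14%, and 7–8% when that correlation is −0.3.

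A reader might also infer that the preoperative score is wasted. It is not: it serves improvement over baseline and, on a natural reading, the repeated-measures ANOVA. Even in the correlation a change score is not excluded, because the satisfaction variable is undefined.

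The two weaknesses should not be added together. The power gain is calculated without deficit confounding. With confounding, the raw test can reject more often than the adjusted one, and the problem is then bias, not missed detection. The deficit is also a subjective estimate, used in the plan only as an entry threshold.

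None of this removes the gain from baseline adjustment, or the value of a deficit-adjusted estimate beside the raw one.

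**Conclusion.** The point holds in limited form. The only stated volume-satisfaction analysis is unadjusted and leaves instrument and visit open. It omits a preoperative score that is already collected, and it is open to confounding by deficit size.

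The precision gain is about 13 points of power at a pre-post correlation of 0.5 and about 3 at 0.3, against a loss of about 1 if the score is uninformative. This assumes a standardised effect of 0.35, 40 evaluable women and no deficit effect. The confounding risk runs from about 9% to 45% false positives under the assumed inputs. The direction is plausible from the plan's own definitions, but the size is unknown.

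The documents do not support saying that a positive coefficient would be spurious, nor would they support reading one as evidence that retained volume drives satisfaction. With 40 women, a model including deficit remains exploratory.

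**What to change.** Replace the sentence in the Statistical Analysis Plan with:

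> Week-8 BREAST-Q Satisfaction with Breasts, and separately the week-8 10-point score, will be regressed on week-8 MRI volume retention with the preoperative BREAST-Q score as a covariate. The retention coefficient and partial correlation will be reported with 95% CI. An exploratory sensitivity analysis will add the surgeon's percentage deficit. The unadjusted Pearson correlation is descriptive and will not be read as evidence that retained volume drives satisfaction.

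Show the estimates with and without deficit side by side, since baseline adjustment alone does not remove deficit confounding. The preoperative BREAST-Q score can serve as the covariate for both outcomes.

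The cost is a few lines of text and one numeric field on the case record form for the deficit estimate already needed for entry. No visit or procedure changes. The statistical cost is about 1 point of power for an uninformative baseline score, and about 4 to 13 points in the sensitivity analysis if neither covariate matters, mainly because deficit is collinear with retention. The plan is written in the past tense; if outcome data have already been examined, label the added models post hoc.
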